3.3.7 Sample Size

Approximately 180 participants will be treated with sabestomig, with up to 52 participants in Part A (Dose Escalation) and participants in Part B (Dose Expansion).

Additional participants may be enrolled if additional dose levels, expansion cohorts, treatment schedules are explored, or participants require replacement for any reason.

Further details are provided in section 9.2 of the protocol.

3.3.7.1 Dose escalation: mTPI-2 (Part A)

The cohort size (3-12) in Part A is based on mTPI-2 dose escalation method and clinical consideration. The modified toxicity probability interval-2 (mTPI-2) employs a simple beta-binomial Bayesian model (Guo et al., 2017

). The prior distribution for all dose levels is Beta(1,1). The posterior distribution for all dose levels is Beta(1+a, 1+b), where a, and b are the number of participants with and without a dose limiting toxicity (DLT) at the current dose level, respectively. The posterior density of the toxicity probability is divided into multiple intervals with equal length. These intervals are categorized as underdosing (below), proper dosing (equivalent), and overdosing (above) in terms of toxicity. The underdosing interval corresponds to a dose escalation, overdosing corresponds to a dose de-escalation, and proper dosing corresponds to staying at the current dose. Given an interval and a probability distribution, the unit probability mass of that interval is defined as the probability of the interval divided by the length of the interval. The design for the dose-escalation phase of the study uses a target (DLT) rate of \(^{12}\)% and an equivalence for dose-escalation/de-escalation decisions as well as maximum interval CC tolerated dose (MTD) determination. A dose level is considered unsafe, with no additional participants enrolled at that dose level, if it has an estimated 80% or more probability of exceeding the target DLT rate of with at least participants treated and evaluated at that dose level.

After the escalation phase is completed, DLT rates at each dose level are estimated by isotonic regression (Ji et al, 2010). The weighted least squares regression model conditional on monotonic non-decreasing DLT rates with increasing dose and use the empirical (observed) DLT rates at each dose level as responses and sample sizes at each dose level as weights, along with the pool adjacent violators algorithm (PAVA) to estimate the DLT rate at each dose level using available software (eg, Cytel EAST or the function pava() from the R package 'ISO'). Given the DLT estimates for each dose level, the MTD is selected from all tried dose levels that have not been previously declared to be unsafe with a "de-escalate to the previous lower dose and the current dose is never used again due to unacceptable toxicity" (DU) decision according to the mTPI-2 decision table. With this constraint, the MTD is determined as the dose level with the DLT estimate closest to the target toxicity level of "".

For specific dose escalation rules, refer to protocol Section 6.6.1.2.

3.3.7.2 Accelerated Titration Design (ATD)

[figure not shown]
For dose levels < 225 mg (Cohorts 1 to 4), dose escalation will follow an ATD and will be single participant cohorts. Cohorts 5, 6, 7, and the optional last cohort, Cohort 8, will follow an mTPI-2 and will consist of 3 to 12 participants. The enrolled participants must complete the DLT evaluation period before a dose escalation decision is made by the SRC. At any

ATD dose level, dose escalation will switch from ATD dose escalation to the mTPI-2 dose escalation algorithm if the initially enrolled participant has any of the following during the DLT evaluation period:

- Any DLT.
- Any ≥ Grade 2 TEAE.

Once the mTPI-2 algorithm is triggered, all further dose escalation will follow mTPI-2 algorithm.

3.3.7.3 Part B Dose Expansion

For details, please refer to Sections 9.2 and 9.5 of the protocol.

4 STATISTICAL ANALYSIS

This section provides information on definitions, derivation and analysis/data presentation per domain.

4.1 Study Population

The domain study population covers participant disposition, analysis sets, protocol deviations, demographics, baseline characteristics medical history, prior and concomitant medication and study drug compliance.

4.1.1 Participant Disposition and Completion Status

4.1.1.1 Definitions and Derivations

Participants enrolled/screened is defined as agreement to participate in the clinical study following completion of the informed consent process by the participant or their legally authorized representative. Completion of study is defined in protocol Section 4.4.

4.1.1.2 Presentation

Participant disposition will be summarized and listed for all participants enrolled by dose level/cohort as defined by the current relevant tables, figures, listings (TFL) standards. Screen failures and reason for screen failures will be reported for the overall category only. The number and percentage of participants for the following categories will be summarized if applicable:

- Participants screened;
- Screen failures;
- Participants assigned to treatment;
- Participants assigned to treatment, but were not treated;
- Participants who started treatment;
- Participants ongoing treatment at data cut-off (DCO);
- Participants who withdrew;
- Participants who discontinued treatment;
- Participants ongoing study at DCO.

Disposition due to global/country situation may be summarized The number and percentage of participants for the following summaries will be presented:

- Participants who discontinued treatment due to global/country situation;
- Participants who withdrew from study due to global/country situation.

The study disruptions due to the global/country situation are also summarized as a separate table

4.1.2 Analysis Sets

4.1.2.1 Definitions and Derivations

For the definitions of each analysis set, refer to Section 3.2.

4.1.2.2 Presentation

The analysis sets will be summarized by dose level /cohort. Any exclusions from analysis sets will be listed.

4.1.3 Protocol Deviations

4.1.3.1 Definitions and Derivations

Protocol deviations are defined in Section 3.3.5.

4.1.3.2 Presentation

The incidence of IPDs will be summarized by deviation categories for the full analysis set (FAS). The number and percentage of participants in the following categories will be summarized:

- Number of participants with at least 1 IPD
- If applicable, number of participants with at least 1 global/country related IPD
- If applicable, number of participants with at least 1 IPD, excluding global/country related IPDs.

A listing will be provided with IPD details.

4.1.4 Demographics

4.1.4.1 Definitions and Derivations

Age will be grouped into the following categories:

- Age group (standard): < 18, ≥ 18 < 65, and ≥ 65 years.
- Age group (disease setting): ≥ 16 < 25, ≥ 25 < 50, ≥ 50 < 65, ≥ 65 < 75, and ≥ 75 years.

Each race category counts participants who selected only that category.

4.1.4.2 Presentation

Demographics will be summarized and listed based on the FAS by dose level/ cohort. The following will be summarized: age, age group, sex, race, ethnicity, and country.

4.1.5 Baseline Characteristics

4.1.5.1 Definitions and Derivations

Body mass index (BMI) will be derived as:

$$BMI\left(\frac{kg}{m^2}\right) = \frac{weight(kg)}{height(m)^2}$$

4.1.5.2 Presentation

Baseline characteristics will be listed and summarized for the FAS by dose level/cohort. The following will be summarized: height (cm), weight (kg) and BMI (kg/m²).

Participant characteristics may further be summarized separately for all participants in the FAS who had confirmed or suspected COVID-19 infection. If less than 5 participants had confirmed or suspected COVID-19 infection, this may be presented in a listing rather than being summarized.

4.1.6 Disease Characteristics

4.1.6.1 Definitions and Derivations

Time from original diagnosis to first dose will be calculated as: (Date of first dose – date of original diagnosis) +1 / (365.25/12).

4.1.6.2 Presentation

Disease characteristics at baseline will be summarized and listed for all participants in the FAS by dose level/cohort as defined by the current relevant TFL standards.

Summaries will be produced that present:

- Eastern Cooperative Oncology Group (ECOG) performance status
- Hodgkins Lymphoma Subtype (histology)
- Hodgkins Lymphoma Subtype
- Hodgkins Lymphoma status after the last line of therapy
- Disease stage (revised Ann Arbor classification)
- Ann Arbor classification subdivision
- Presence of bulky disease
- Presence of extra nodal disease

4.1.7 Medical History

4.1.7.1 Definitions and Derivations

Medical history will be coded using the latest version of the Medical Dictionary for Regulatory Activities (MedDRA).

4.1.7.2 Presentation

Medical history and relevant surgery will be listed and summarized for the FAS set by dose level/cohort as defined by the current TFL standards.

Summaries of the number and percentage of participants who have had prior disease-related treatments, including autologous HSCT will be presented.

The number and percentage of participants who have had prior anti-cancer therapy for cHL will be summarized by Anatomical Therapeutic Chemical (ATC) classification and generic drug name, coded by World Health Organization (WHO) – Drug dictionary (WHODrug Global B3 Sep 2021 or later).

Summaries for the number and percentage of participants who had a certain number of lines of therapies and the best response on most recent line of therapy will be produced.

Summaries on participants' medical history (prior and ongoing) by System Organ Class (SOC) and Preferred Term (PT) will be produced.

4.1.8 Prior and Concomitant Medications/Procedures

4.1.8.1 Definitions and Derivations

For the purpose of inclusion in prior and/or concomitant medication, procedures or therapy summaries, incomplete medication or radiotherapy start and stop dates are imputed as detailed in Section 3.3.6.

Prior medications, concomitant and post-treatment medications or procedures are defined based on imputed start and stop dates as follows:

- Prior medications/procedures are those taken prior to study treatment with a stop date prior to the first dose of study treatment.
- Concomitant medications/procedures are those with a stop date or ongoing on or after
 the first dose date of study treatment, and must have started prior to or during treatment so
 there is at least one day in common with the study treatment.
- Post-treatment medications/procedures are those with a start date after the last dose date
 of study treatment plus 90 days.

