- Baseline is the last non-missing value obtained prior to the first dose/administration of any study treatment and any information taken after first dose/administration of study treatment is regarded as post-baseline information. If two visits are equally eligible to assess participant status at baseline (eg. screening and baseline assessments both on the same date prior to first dose/administration with no washout or other intervention in the screening period), the average is taken as the baseline value. For non-numeric laboratory tests (ie, some of the urinalysis parameters) where taking an average is not possible then the best value is taken as baseline as this is the most conservative. In the scenario where there are two assessments on Day 1 prior to first dose, one with time recorded and the other without time recorded, the one with time recorded is selected as baseline. Where safety data are summarized over time, study day is calculated in relation to date of first treatment. For assessments on the day of first dose where time is not captured, a nominal pre-dose indicator, if available, serves as sufficient evidence that the assessment occurred prior to first dose. Assessments on the day of the first dose where neither time nor a nominal pre-dose indicator are captured is considered prior to the first dose if such procedures are required by the protocol to be conducted before the first dose. If no value exists before the first dose/administration, then the baseline value is treated as missing.
- In all summaries, change from baseline endpoints will be calculated as the post-treatment value minus the value at baseline. The percentage change from baseline will be calculated as (post-baseline value baseline value) / baseline value × 100. For any endpoint subjected to log transformation, the change from baseline calculated and summarized on the log scale will be back-transformed and presented as a 'baseline scaled ratio' (BSR). Percentage change will be then calculated as (BSR 1) × 100.
- Unless stated otherwise, two-sided confidence intervals are produced at 95%.

– ed. 3.0

- For the purposes of summarizing safety data assessed at visits, in addition to baseline
 data, only on treatment data will be included in the summary tables. On treatment
 data will be defined as data after the first dose of IP and with assessment date up to
 and including the date of last IP + 90 days, and prior to the start of any subsequent
 cancer therapy.

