4.1.8.2 Presentation

The number and percentage of participants who took prior and concomitant medications or had concomitant procedures will be summarized by ATC classification codes and the generic term coded by WHO Drug Global B3 Sep 2021 or later for the FAS by dose level/cohort.

All prior, concomitant and post study intervention medication data will be listed.

Missing coding terms will be listed and summarized as "Not coded".

In addition, post study drug - anti-cancer therapies for cHL post study drugs - HSCT and post study drugs - radiotherapies will be listed as well as summarized (number and percentage of subjects).

4.2 **Endpoint Analyses**

This section covers details related to the endpoint analyses such as primary, secondary, other endpoints including sensitivity and supportive analyses.

Table 2 Endpoint Analyses					
Statistical category	Endpoint	Population	Population level summary (analysis)	Details in section	
Part A Dose Escal	ation				
Objective 1: To a	ssess the safety and tolerab	ility of sabestomi	g in participants with	r/r cHL	
Primary	AEs, imAEs, SAEs, AEs leading to discontinuation of sabestomig, Laboratory data changes, vital signs changes and ECG changes	Safety analysis set	Descriptive statistics on safety endpoints	4.5.2 (AEs) 4.5.4 and 4.5.5 (laboratory data) 4.5.6 (vital signs) 4.5.7 (ECG)	
Primary	Incidence of dose- limiting toxicities	Safety analysis set	Dose-limiting toxicities	4.5.10.1 DLT	
Part B Dose Expa Objective 2: To a	nsion (all) ssess the safety and tolerab	ility of sabestomi	g in participants with	r/r cHL	
Primary	AEs, imAEs, SAEs, AEs leading to discontinuation of sabestomig Laboratory data changes, vital signs changes and ECG changes	Safety analysis set	Descriptive statistics on safety endpoints	4.5.2 (AEs) 4.5.4 and 4.5.5 (laboratory data) 4.5.6 (vital signs) 4.5.7 (ECG)	
Part B Dose Expa Objective 3: To a (anti-PD-1/PD-L1	ssess the preliminary antit	ımor activity of s	abestomig in participa	nnts with r/r cHL	
Primary	Objective Response Rate [a]	Response evaluable set	ORR and 95% CI	4.2.2	
Objective 4: To a	Part B Dose Expansion (B2) Objective 4: To assess the preliminary antitumor activity of sabestomig in participants with r/r cHL (anti-PD-1/PD-L1 naïve)				
Primary	Complete Response Rate [a]	Response evaluable set	CR rate and 95% CI	4.2.3	
Part A Dose Escalation Objective 5: To assess the preliminary antitumor activity of sabestomig in participants with r/r cHL					

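### SAP 4.1.8.1 puts medications newly started between the end of treatment and last dose + 90 days in no class, so the concomitant-medication summary omits them

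*SAP*

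**What the plan says.** SAP 4.1.8.1 sorts medications and procedures into three classes.

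- **Prior:** stopped before the first dose.
- **Concomitant:** ongoing, or with a stop date, on or after "the first dose date of study treatment, and must have started prior to or during treatment so" that "there is at least one day in common with the study treatment".
- **Post-treatment:** "Post-treatment medications/procedures are those with a start date after the last dose date" "of study treatment plus 90 days".

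SAP 4.1.8.2 then states what is shown. For tables: "The number and percentage of participants who took prior and concomitant medications or had concomitant procedures will be summarized by ATC classification codes" and generic term. For listings: "All prior, concomitant and post study intervention medication data will be listed". Anticancer therapy, stem cell transplant and radiotherapy given after study drug have their own listing and summary. No summary is planned for other post-treatment medications.

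SAP 4.5.2.1 counts an adverse event as treatment-emergent if it starts or worsens from the first dose through 90 days after the last dose, before any subsequent cancer therapy. Protocol 8.3.1 collects adverse events over the same 90 days. Protocol 6.5 requires every medication received during the study to be recorded, and the follow-up schedule (protocol Table 4) has a row for concomitant medications.

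**The concern.** The concomitant class closes when treatment ends, and the post-treatment class does not open until day 91 after the last dose. New starts in between are recorded but have no class, and the medication table is built on the classes.

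That interval coincides with the safety follow-up. Immune-mediated events are a named primary safety endpoint in both parts of the trial. SAP 4.5.2.1 itself describes the events of special interest as ones that may call for steroids, other immunosuppressants or hormone replacement. If a participant stops sabestomig and later starts such a drug for a late event, the event appears in the treatment-emergent tables but the drug is absent from the medication table. A reader setting the two side by side would see less use of these drugs than actually occurred.

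**Working it through.** The plan gives no figure here to reproduce. The check is to classify each possible start day, with the date of the last dose as day 0, under the SAP's own rules.

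**Inputs**

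- The concomitant class takes starts up to the end of treatment, day T (SAP 4.1.8.1). T is not defined for medications.
- The post-treatment class takes starts after day 90 (SAP 4.1.8.1).
- Three values of T can be taken from the SAP:
  - 0, the last dose itself.
  - 20, from the exposure rule in SAP 4.5.1.1 (last dose + 21 − 1).
  - 90, from the on-treatment window in SAP 3.3.1, which runs up to "and including the date of last IP + 90 days, and prior to the start of any subsequent" cancer therapy.

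**Formula:** unclassified start days = days T + 1 to 90, a count of 90 − T.

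| Reading of treatment end | T | Unclassified start days | Count |
|---|---|---|---|
| Last dose | 0 | 1 to 90 | 90 |
| Exposure rule | 20 | 21 to 90 | 70 |
| On-treatment window, no new cancer therapy by day 90 | 90 | none | 0 |

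**Which reading fits the text.** SAP 3.3.1 sets its window for safety data assessed at visits, not for medications. A drug first taken on day 60 after the last dose does not naturally have a day in common with study treatment. The third reading therefore has to be imported from elsewhere. Even then it closes the gap only for some participants, because that window stops at subsequent cancer therapy. If new therapy began on day 40, a supportive drug started on any of days 40 to 90 (90 − 40 + 1 = 51 days) would still have no class.

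**Consequence for outputs.** An unclassified item is not in the summary, since only prior and concomitant items are summarized. Relabelling it as post-treatment would not bring it in either, because general post-treatment medications are only listed. It reaches the table only if the concomitant class is extended or a separate follow-up summary is added.

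**The case against.** The best defence is that the authors meant the concomitant class to follow the adverse event phases. The 90-day offset for post-treatment medications matches the start of the post-treatment adverse event phase in SAP 4.5.2.1. SAP 3.3.6 also treats the treatment-emergent status of adverse events and of concomitant medications as the same kind of decision when dates are imputed. On that reading the gap is 0 days for a participant who takes no new cancer therapy by day 90. This is a plausible account of the intent, but SAP 4.1.8.1 does not say it, and its requirement of a shared day with study treatment points the other way.

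The defence does hold on several points:

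- **Listings.** A reader might infer that these medications also vanish from the listings. The documents do not support that. SAP 4.1.8.2 lists medication data after study intervention, which is not the defined post-treatment term and in plain words covers anything after the last dose. Loss would follow only if the phrase were programmed as the narrower class.
- **Continuing medications.** A drug started before or during treatment and carried into follow-up remains concomitant. Only new starts are affected.
- **Later cancer treatment.** Anticancer therapy, transplant and radiotherapy are reported separately.
- **No planned link to events.** The medication table is by drug class and generic term. No planned table of treatments for immune-mediated events is being lost.

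A reader might also want to express the gap as a share of the treatment-emergent period. That share depends on an assumed number of doses. With six doses the last falls on day 1 + 5 × 21 = 106, the period is 106 + 90 = 196 days, and the share is 90/196 = 46% (or 70/196 = 36%). With the maximum of 35 cycles the last dose is on day 1 + 34 × 21 = 715, and the share is 90/805 = 11%. These are shares of calendar time and say nothing about how many medications or participants are affected.

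**Conclusion.** The point holds as a classification gap in SAP 4.1.8.1. Read literally, 90 start days after the last dose have no class, or 70 if treatment is taken to end under the exposure rule. It rests on reading the concomitant definition as written; no definition of treatment end specific to medications is given. The effect is an incomplete concomitant-medication summary for new starts in a window whose adverse events are counted as treatment-emergent. The documents give no basis for estimating how many participants would be affected.

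The issue is minor. It does not change adverse event or immune-mediated event counts, response rates or time-to-event endpoints, and no loss from listings is shown. It still merits correction, because otherwise programmers must guess the rule.

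**What to change.** In SAP 4.1.8.1, set one boundary: the earlier of last dose + 90 days and the day before subsequent anticancer therapy starts. Then:

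- **Concomitant:** taken or ongoing on or after the first dose, with a start date on or before the boundary. Drop the requirement of a day in common with study treatment.
- **Post-treatment:** any start after the boundary.

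With the prior class unchanged, every item falls in exactly one class. The concomitant class then matches the treatment-emergent window. Both edits are needed. If the concomitant class ended at new anticancer therapy while post-treatment still began after day 90, a drug started on day 50 following new therapy on day 40 would remain unclassified.

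The cost is a rewording of two definitions and the matching derivation. No new data, sample size change or added analysis is required.

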4.1.8.2 Presentation

The number and percentage of participants who took prior and concomitant medications or had concomitant procedures will be summarized by ATC classification codes and the generic term coded by WHO Drug Global B3 Sep 2021 or later for the FAS by dose level/cohort.

All prior, concomitant and post study intervention medication data will be listed.

Missing coding terms will be listed and summarized as "Not coded".

In addition, post study drug - anti-cancer therapies for cHL post study drugs - HSCT and post study drugs - radiotherapies will be listed as well as summarized (number and percentage of subjects).

4.2 **Endpoint Analyses**

This section covers details related to the endpoint analyses such as primary, secondary, other endpoints including sensitivity and supportive analyses.

Table 2 Endpoint Analyses					
Statistical category	Endpoint	Population	Population level summary (analysis)	Details in section	
Part A Dose Escal	ation				
Objective 1: To a	ssess the safety and tolerab	ility of sabestomi	g in participants with	r/r cHL	
Primary	AEs, imAEs, SAEs, AEs leading to discontinuation of sabestomig, Laboratory data changes, vital signs changes and ECG changes	Safety analysis set	Descriptive statistics on safety endpoints	4.5.2 (AEs) 4.5.4 and 4.5.5 (laboratory data) 4.5.6 (vital signs) 4.5.7 (ECG)	
Primary	Incidence of dose- limiting toxicities	Safety analysis set	Dose-limiting toxicities	4.5.10.1 DLT	
Part B Dose Expa Objective 2: To a	nsion (all) ssess the safety and tolerab	ility of sabestomi	g in participants with	r/r cHL	
Primary	AEs, imAEs, SAEs, AEs leading to discontinuation of sabestomig Laboratory data changes, vital signs changes and ECG changes	Safety analysis set	Descriptive statistics on safety endpoints	4.5.2 (AEs) 4.5.4 and 4.5.5 (laboratory data) 4.5.6 (vital signs) 4.5.7 (ECG)	
Part B Dose Expa Objective 3: To a (anti-PD-1/PD-L1	ssess the preliminary antit	ımor activity of s	abestomig in participa	nnts with r/r cHL	
Primary	Objective Response Rate [a]	Response evaluable set	ORR and 95% CI	4.2.2	
Objective 4: To a	Part B Dose Expansion (B2) Objective 4: To assess the preliminary antitumor activity of sabestomig in participants with r/r cHL (anti-PD-1/PD-L1 naïve)				
Primary	Complete Response Rate [a]	Response evaluable set	CR rate and 95% CI	4.2.3	
Part A Dose Escalation Objective 5: To assess the preliminary antitumor activity of sabestomig in participants with r/r cHL					
Secondary	Complete Response Rate [b]	Response evaluable set	CR rate and 95% CI	4.2.3	

Table 2 Endpoint Analyses						
Statistical category	Endpoint	Population	Population level summary (analysis)	Details in section		
Secondary	Objective Response Rate [b]	Response evaluable set	OR rate and 80% (Л 4.2.2		
Secondary	Duration of Response [b]	Response evaluable set	Median DoR and i two-sided 95% CI estimated using Kaplan-Meier method	ts 4.2.4		
Secondary	Duration of Complete Response [b]	Response evaluable set	Median DoCR and its two-sided 95% CI estimated using Kaplan-Meier method			
Secondary	Progression Free Survival at 12 and 24 months [b]	Full analysis set	Median PFS and it two-sided 95% CI estimated using Kaplan-Meier method	4.2.6		
Secondary	Overall Survival at 12 and 24 months	Full analysis set	Median OS and its two-sided 95% CI estimated using Kaplan-Meier method	4.2.7		
Part B Dose Expa Objective 6: To f r/r cHL	nnsion further assess the prelimina	ry antitumor acti	vity of sabestomig i	n participants	with	
Secondary			Response evaluable set	Median DoR and its two- sided 95% CI estimated using Kaplan- Meier method	4.2.4	
Secondary	Duration of Complete Resp	oonse [a]	Response evaluable set	Median DoCR and its two-sided 95% CI estimated using Kaplan-	4.2.5	

- ed. 3.0

Table 2 Endpo	Table 2 Endpoint Analyses						
Statistical category	Endpoint	Population	Population level summary (analysis)	Details in section	ı		
				Meier method			
Secondary	Progression Free Su months [a]	rvival at 12 and 24	Full analysis set	Median PFS and its two- sided 95% CI estimated using Kaplan- Meier method	4.2.6		
Secondary	Overall Survival at	12 and 24 months	Full analysis set	Median OS and its two- sided 95% CI estimated using Kaplan- Meier method	4.2.7		

Part A Dose Escalation and Part B Dose Expansion

Objective 7:

- To assess the PK of sabestomig in participants with r/r cHL
- To assess the immunogenicity of sabestomig in participants with r/r cHL

Secondary	PK of sabestomig	PK analysis set	Descriptive statistics on PK endpoints	4.3
Secondary	Immunogenicity of sabestomig	Immunogenicity analysis set	Descriptive statistics of anti-drug antibodies	4.4

[[]a] Based on Blinded Independent Central Review (BICR) assessments based on Modified Lugano criteria 2014 (Chelson et al 2014).

The images of participants treated with RP2D in part A will undergo a retrospective central review to be combined with Part B BICR assessments for efficacy analyses.

cHL: classical Hodgkin Lymphoma; DoR: Duration of Response; DoCR: Duration of Complete Response; OS: Overall Survival; PFS: Progression-free Survival; PK: pharmacokinetic(s); RECIL: Response-evaluation Criteria in Lymphoma; r/r cHL: relapsed/refractory cHL.

[[]b] Based on investigator assessments (as entered in the database) based on Modified Lugano criteria 2014 (Chelson et al 2014) and RECIL criteria (Younes et al, 2017).

Additionally, supportive secondary efficacy analyses for part B, as done for part A, including objective and complete response rate, duration of response, and PFS at 12 and 24 months will be based on Investigator assessments based on Lugano criteria for malignant lymphoma (Chelson et al 2014) and RECIL criteria (Younes et al, 2017). All efficacy results will be listed

All efficacy analyses will be presented by dose level/cohort.

4.2.1 Primary Safety Endpoints: AEs, immune mediated AEs and serious AEs, laboratory evaluations, vital signs, ECG results Definition and DLTs

Analysis methods for the primary safety endpoints are described in Section 4.5.

